4.2 Statistical and Analytical Methods

4.2.1 Analysis Populations and Analysis Groups

Population of Patients Enrolled [EP]

The population of patients enrolled comprises all patients who voluntarily sign and date an informed consent prior to inclusion into the study and data were captured in the eCRF.

Target Population [TP]

Patients will be included if the following applies:

- Age at least 18 years
- Confirmed CHC with genotype 1 and/or 4 only, receiving combination therapy with the interferon-free ABBVIE REGIMEN \pm RBV. The prescribed ABBVIE REGIMEN needs to be known.
- Have voluntarily signed and dated an informed consent prior to inclusion into the study
- Must not be participating or intending to participate in a concurrent interventional therapeutic trial

Core Population [CP]

The core population is defined as all patients of the target population (TP) (definition see above), who are adequately treated according to the standard of care and within local label recommendations for their specific disease characteristics (cirrhotic status, genotype). The following patients will be excluded from the CP:

- Patients with unknown fibrosis status
- Cirrhotic patients with genotype 1a not receiving ribavirin
- Patients with genotype 1 for whom 2DAA instead of 3DAA is prescribed
- Patients with genotype 4 not receiving RBV

Non-Core Population [NCP]

Patients in the TP who are not in the CP.

Core Population with Sufficient Follow-up [CPSFU {12, 24}]

In addition, the core population with sufficient follow-up data regarding SVR12 or SVR24, respectively, is defined as all CP patients,

- who have evaluable HCV RNA data ≥ 70 days or >126 days, respectively, after the last actual dose of the ABBVIE REGIMEN
- or a HCV RNA value ≥ 50 IU/mL at the last measurement post-baseline
- or had HCV RNA <50 IU/mL at the last measurement post-baseline, but no HCV RNA measurement ≥ 70 days or >126 days, respectively, after the last actual dose of the ABBVIE REGIMEN due to reasons related to safety (e.g. dropped out due to adverse event) or virologic failure (e.g. virologic failure such as relapse is reported in the electronic case report form (eCRF) but date and value of the corresponding HCV RNA test is missing).

This means only (1) patients who had virological response at their last on-treatment or post-treatment measurement, but had no post-treatment HCV RNA measurements ≥ 70 days or >126 days, respectively, for reasons not related to safety or effectiveness (e.g. lost-to-follow-up or patient not willing to perform an additional HCV RNA test ≥ 70 days or >126 days post-treatment, respectively) and (2) patients who had no post-baseline HCV RNA measurements for reasons not related to safety or effectiveness, and (3) patients with missing end of treatment date for reasons not related to safety or effectiveness, will be excluded from this analysis.

Safety population [SP]

The safety population is defined as all enrolled patients who received at least one dose of the ABBVIE REGIMEN. The prescribed ABBVIE REGIMEN needs to be known.

EP and TP analysis groups

The EP/TP analysis groups are defined according to the patient's fibrosis status and genotype/subtype and standard summaries are structured as follows:

- Total (regardless of cirrhosis status)
 - (1) Total (regardless of genotype)
 - (2) G1 (Total)
 - (3) G1a (including mixed G1 subtypes and patients with G1 unknown subtype)
 - (4) G1b
 - (5) G4 (non-G1)
 - (6) Other/unknown genotype (*only for EP*)
- Patients with cirrhosis
 - (7) Total (regardless of genotype)
 - (8) G1 (Total)
 - (9) G1a (including mixed G1 subtypes and patients with unknown G1 subtype)
 - (10) G1b
 - (11) G4 (non-G1)
 - (12) Other/unknown genotype (*only for EP*)
- Patients without cirrhosis
 - (13) Total (regardless of genotype)
 - (14) G1 (Total)
 - (15) G1a (including mixed G1 subtypes and patients with unknown G1 subtype)
 - (16) G1b
 - (17) G4 (non-G1)
 - (18) Other/unknown genotype (*only for EP*)
- Patients with unknown fibrosis status
 - (19) Total (regardless of genotype)
 - (20) G1 (Total)
 - (21) G1a (including mixed subtypes and patients with unknown subtype)
 - (22) G1b
 - (23) G4 (non-G1)
 - (24) Other/unknown genotype (*only for EP*)

(HCV genotypes will be combined as follows: G1 [total], G1a*, G1b, G4 [non-G1]. * includes mixed or other G1 subtypes and patients with unknown G1 subtypes.

Most recent stage of liver fibrosis will be categorized as follows: No cirrhosis/Transition to cirrhosis, Cirrhosis. Only one method should be selected by the physicians to report stage of fibrosis. Nevertheless, if there are multiple answers the following priority will be used:

1. Biopsy,
2. Non-invasive,
3. Clinical/best guess.

For biopsy as assessment method the respective categories are defined as follows:

- “No cirrhosis” is defined by “No fibrosis”, “Mild/minimal fibrosis”, “Moderate fibrosis”
- “Transition to cirrhosis” is defined by “Advanced Fibrosis”
- “Cirrhosis” is defined by “Cirrhosis”.)

CP analysis groups and related treatment regimens

The CP analysis groups are defined according to the patient's fibrosis status and genotype/subtype. The standard summaries by CP analysis groups in the CP and CPSFU population are structured follows (is not specified otherwise):

- Total (regardless of cirrhosis status)
 - (1) Total (regardless of genotype)
 - (2) G1 (Total)
 - (3) G1a (including mixed subtypes and patients with unknown subtype)
 - (4) G1b
 - (5) G4 (non-G1)
- Patients with cirrhosis
 - (6) Total (regardless of genotype)
 - (7) G1 (Total)
 - (8) G1a (including mixed subtypes and patients with unknown subtype)
 - (9) G1b
 - (10) G4 (non-G1)
- Patients without cirrhosis
 - (11) Total (regardless of genotype)
 - (12) G1 (Total)
 - (13) G1a (including mixed subtypes and patients with unknown subtype)
 - (14) G1b
 - (15) G4 (non-G1)

SP analysis groups

The SP analysis groups are defined according to the treatment regimen and patient's fibrosis status. The standard summaries by SP groups in the safety population are as follows (if not specified otherwise):

- Total (regardless of cirrhosis status)
 - (1) Total
 - (2) 2DAA w/o RBV
 - (3) 2DAA + RBV
 - (4) 3DAA w/o RBV
 - (5) 3DAA + RBV
- Patients with cirrhosis
 - (6) Total
 - (7) 2DAA w/o RBV
 - (8) 2DAA + RBV
 - (9) 3DAA w/o RBV
 - (10) 3DAA + RBV
- Patients without cirrhosis
 - (11) Total
 - (12) 2DAA w/o RBV
 - (13) 2DAA + RBV
 - (14) 3DAA w/o RBV
 - (15) 3DAA + RBV
- Patients with unknown fibrosis status
 - (16) Total
 - (17) 2DAA w/o RBV
 - (18) 2DAA + RBV
 - (19) 3DAA w/o RBV
 - (20) 3DAA + RBV

(2DAA - paritaprevir/r-ombitasvir, 3 DAA - paritaprevir/r-ombitasvir + dasabuvir, RBV – ribavirin taken, w/o RBV – no ribavirin taken)

NCP analysis groups

The summary tables for the NCP will only show the data pooled for all patients in the NCP without any subgrouping by genotype and/or fibrosis status.

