## **9.7 Data Analysis**

### **9.7.1 Analysis Population, Time Windows and Handling of Missing Data**

The target population (TP) is defined as all patients who fulfill the criteria specified in Section 9.2.1. The core population (CP) is defined as all patients of the TP, who have started the treatment combination recommended in the current local label for their disease characteristics. Patients not receiving the treatment recommended in the local label will be summarized in the non-core population (NCP). In addition, the core population with sufficient follow-up data (CPSFU) is defined as all CP patients, who fulfil one of the following criteria:

- (1) evaluable HCV RNA data  $\geq 70$  days after the last actual dose of the ABBVIE REGIMEN (i.e. data within the SVR12 time window)
- (2) a HCV RNA value  $\geq 50$  IU/mL at the last measurement post-baseline (i.e. no virological response achieved at the last measurement on-treatment or post-treatment)
- (3) HCV RNA  $< 50$  IU/mL at the last measurement post-baseline, but no HCV RNA measurement  $\geq 70$  days after the last actual dose of the ABBVIE REGIMEN due to reasons related to safety (e.g. dropped out due to AE) or incomplete efficacy information (e.g. virologic failure such as relapse is reported in the eCRF but date and value of the corresponding HCV RNA test is missing). This means only patients who had virological response at their last on-treatment or post-treatment

---

Confidential Information

No use or disclose outside AbbVie is permitted without prior written authorization from AbbVie

---

measurement, but had no HCV RNA measurements  $\geq 70$  days post-treatment for reasons not related to safety or effectiveness (e.g. lost-to-follow-up or patient not willing to perform an additional HCV RNA test  $\geq 70$  days post-treatment) will be excluded from this analysis.

The Safety Population (SP) is defined as all patients who received at least one dose of the ABBVIE REGIMEN.

In accordance with the non-interventional nature of the study all HCV RNA measurements will be performed at the sole discretion of the physician and all HCV RNA measurements have to be entered into the eCRF. All recorded HCV RNA values will be assigned to appropriate time points (baseline, on-treatment visits, EoT visit, post-treatment visits). The time windows for the assignments will be specified in the statistical analysis plan (SAP).

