4.2.3 Handling of missing data

No data will be imputed for any effectiveness or safety analyses except for the analyses of the HCV RNA endpoints and certain PRO endpoints. The discussion of missing data imputation for the PRO endpoints is included in section 4.2.7.2.2.

HCV RNA values will be selected for an RVR, EOTR and SVR analysis based on visit windows as defined in Table 2. When there is no HCV RNA value in a visit window based on defined visit windows, the closest values before and after the window, regardless of the value chosen for the subsequent and preceding window, will be used for the flanking imputation described below. For

analysis of RVR, EOT and SVR, if a subject has a missing HCV RNA value at a post-Day 1 visit but with undetectable or unquantifiable (LLoD or LLoQ \leq 50 IU/mL) HCV RNA levels at both the preceding value and succeeding value, the HCV RNA level will be considered undetectable or unquantifiable, respectively, at this visit for this subject. In addition, if a subject has an unquantifiable HCV RNA level at the preceding value and an undetectable HCV RNA level at the succeeding value, or vice versa, the HCV RNA level will be imputed as unquantifiable at this visit for this subject.

For analyses of RVR, subjects still missing a value for the visit after flanking imputation will be considered as a failure. For EoTR and SVR analysis, if there is no value in the appropriate window after flanking imputation but there is an HCV RNA value after the window, then it will be imputed into the EoTR or SVR window respectively. Subsequent to this flanking and backward imputation, if the HCV RNA value remains missing at a specific time point, then the subject will be considered as virological failure at this time point (i.e., not undetectable or unquantifiable).

If a subject starts another treatment for HCV, then all HCV RNA values for this subject measured on or after the start date of the new HCV treatment will be excluded from analyses. The subject will be considered a failure for summaries of viral response at all time points after the start of the new HCV treatment.

Due to the non-interventional nature of this study several different methods for determination of the HCV RNA value can be applied. For the purpose of the statistical analysis, a HCV RNA measurement is considered <50 IU/mL,

- if a PCR test was used

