4.2.7 Analyses of the Objectives

4.2.7.1 Primary Effectiveness Variable

The primary objective of this study is to estimate the SVR12 rates in HCV patients treated according to the ABBVIE regimen.

Therefore the simple percentage of patients achieving SVR12 (for definition see section 4.1.1) will be calculated and a two-sided 95% confidence interval (CI) of the percentage will be computed based on the Wilson's Score method.

The primary effectiveness analysis on clinical outcomes will be performed on all patients in the CP stratified by genotype and cirrhosis status and overall.

In the framework of sensitivity analyses the primary analyses will be repeated for the CPSFU. Furthermore, the SVR12 rates will be also determined for all patients of the NCP.

An overview of Tables is given in Table 7.

The layouts of the tables mentioned above are provided in Part II of the SAP (Table Shells).

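### SAP 4.2.1 puts a core-population patient with no post-baseline HCV RNA, for a safety or effectiveness reason, both outside and inside the CPSFU

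*SAP*

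**What the plan says.** SAP 4.2.1 defines the CPSFU, for SVR12 and SVR24 separately, as CP patients who meet any one of three bullets:

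- Bullet 1: patients "who have evaluable HCV RNA data" at least 70 days (SVR12) or more than 126 days (SVR24) after the last dose.
- Bullet 2: patients whose value is at or above "50 IU/mL at the last measurement post-baseline".
- Bullet 3: patients who "had HCV RNA <50 IU/mL at the last measurement post-baseline" and lack a later value because of safety or virologic failure.

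The next sentence restates the definition as a closed list of exclusions, beginning "This means only (1) patients who had virological response at their last on-treatment or post-treatment measurement". Its second item is "patients who had no post-baseline HCV RNA measurements for reasons not related to safety or effectiveness". Its third concerns a missing end-of-treatment date, again only for unrelated reasons.

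SAP 4.2.3 sets the outcome when nothing can be imputed: "if the HCV RNA value remains missing at a specific time point, then the subject will be considered as virological failure". SAP 4.2.7.1 runs the primary SVR12 analysis in the CP and adds: "In the framework of sensitivity analyses the primary analyses will be repeated for the CPSFU". SAP 4.2.7.2.1 names the CPSFU as the population in which SVR24 is reported.

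Protocol 9.7.1 has equivalent entry criteria. Its closing sentence starts "This means only patients who had virological response at their last on-treatment or post-treatment" and has no item for patients without a post-baseline value.

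**The concern.** The CPSFU is built to set aside losses that say nothing about the drug while keeping patients whose data are missing because of safety or failure. A patient who dies or disappears after an adverse event, never having been sampled after baseline, is the clearest case of the second kind. The two halves of the definition disagree on that patient, and nothing says which half governs.

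The disagreement has a direction. Dropping a patient who would count as a failure leaves the numerator alone and shrinks the denominator, so programming from the bullets can only raise the CPSFU rate. If the choice is left until programming, it may be made with the data in view.

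**Working it through.** **Step 1. Apply both texts to the same patient.** Take a CP patient with no HCV RNA value after baseline, whether on treatment, at end of treatment or in follow-up, for a safety reason.

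| Text | Condition | Result for this patient |
|---|---|---|
| Bullet 1 | value ≥70 days (or >126 days) after last dose | not met |
| Bullet 2 | last post-baseline value ≥50 IU/mL | not met, no such value |
| Bullet 3 | last post-baseline value <50 IU/mL, later data missing for safety or failure | not met, no such value |
| Exclusion (1) | response at last measurement, unrelated reason | does not apply |
| Exclusion (2) | no post-baseline value, unrelated reason | does not apply, the reason is safety |
| Exclusion (3) | missing end-of-treatment date, unrelated reason | does not apply |

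By the bullets the patient is out. By the exclusion list the patient is in. The result is the same if the reason is effectiveness, because bullet 3 again needs a value below 50 IU/mL.

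**Step 2. Outcome if in.** Flanking imputation needs a value on each side of the window, and backward imputation needs a later value. Neither exists, so SAP 4.2.3 makes the patient a virological failure. That status comes from 4.2.3; the sentence in 4.2.1 decides membership only.

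**Step 3. Does the protocol settle it?** No. The criteria in protocol 9.7.1 also require a post-baseline value, and its closing sentence does not list this patient as excluded, so the same conflict is there. The protocol abstract omits the words restricting the last measurement to post-baseline. Read literally, it would admit the patient on a baseline value of 50 IU/mL or more.

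**Step 4. Size.** The documents give no expected CPSFU rate, so there is no planned figure to reproduce. Let x be the responders, n the CPSFU size by the bullets, and k the affected patients. Then

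shift = x/n − x/(n+k) = (x/n) × k/(n+k).

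The 95% interval is Wilson's, as in SAP 4.2.7.1. With p = x/n and z = 1.96, the centre is (p + z²/2n)/(1 + z²/n) and the half-width is z√(p(1−p)/n + z²/4n²)/(1 + z²/n).

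The values x = 47, n = 48 and k are assumptions. They are chosen to be compatible with the 50–55 patients expected in SAP 3.2.

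- For 47/48: centre 0.9437, half-width 0.0527, giving 89.1–99.6%.
- For 47/49: centre 0.9258, half-width 0.0629, giving 86.3–98.9%.
- Shift for k = 1: 0.979 × 1/49 = 0.020.

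| k | Rate if kept as failures | Wilson 95% CI | Bullets (47/48 = 97.9%) minus kept |
|---|---|---|---|
| 0 | 47/48 = 97.9% | 89.1–99.6 | 0 |
| 1 | 47/49 = 95.9% | 86.3–98.9 | 2.0 points |
| 2 | 47/50 = 94.0% | 83.8–97.9 | 3.9 points |
| 3 | 47/51 = 92.2% | 81.5–96.9 | 5.8 points |

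The ends of the enrolment range, with one affected patient and no other failure, agree:

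- 50 patients: 49/49 = 100% (92.7–100) dropped, against 49/50 = 98.0% (89.5–99.6) kept.
- 55 patients: 54/54 = 100% (93.4–100) dropped, against 54/55 = 98.2% (90.4–99.7) kept.

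In a genotype-by-cirrhosis stratum with 10 responders (assumed), one such patient moves 10/10 = 100% (72.2–100) to 10/11 = 90.9% (62.3–98.4).

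**The case against.** The best defence is that the SAP already shows its intent. Exclusion (2) is not in the protocol, so it was added for patients without post-baseline values. It sits directly below the bullets, and a programmer who reads the whole definition can see what was meant. That stands as evidence of intent. It does not remove the conflict, because the bullets are the operative entry rule and were not changed to match.

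The defence is also right that the affected group is narrow. A reader might infer that anyone who stops for an adverse event before the first on-treatment sample is lost. That is not so. A later sample at or beyond day 70 satisfies bullet 1, and a last post-baseline value of 50 IU/mL or more satisfies bullet 2. Patients who discontinue are asked to return for end-of-treatment data (protocol Table 2, note b). Enrolment may take place during the first four weeks of treatment (protocol 9.4.1.1), so some of the earliest stoppers may never enter the study. On the other side, HCV RNA is measured only at the physician's discretion, and SAP 4.2.7.2.1 has a non-response category for death, so such a patient remains possible.

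Finally, the case would not be hidden. Reasons for exclusion from each population are tabulated (SAP 4.2.5), and the CP non-response table has rows for death and premature discontinuation. The study is descriptive with no success threshold, and the intervals above overlap heavily. These points limit the harm. They do not say which rate is the planned one.

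**Conclusion.** The point holds for one defined group: CP patients with no post-baseline HCV RNA at any time, for a safety or effectiveness reason. For them SAP 4.2.1 gives two opposite instructions, and following the bullets biases the CPSFU rates upward. The size is about 2 percentage points per such patient at about 50 patients, more in small strata, and nil if none occurs. The counts are assumptions, since the documents give no figure.

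Two stronger readings are not supported. A reader might infer that the primary result is at risk. It is not, because the primary SVR12 analysis uses the CP, where this patient is a failure under SAP 4.2.3 whichever text is followed. A reader might also infer that the CPSFU is the only other view of SVR12. It is the one labelled as a sensitivity analysis, but SVR12 is also planned for the non-core population and for treatment completers. What is affected is the CPSFU repeat of SVR12 and the SVR24 rate, for which the CPSFU is the named reporting population.

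**What to change.** Add a fourth bullet to the CPSFU definition in SAP 4.2.1: *or had no post-baseline HCV RNA measurement for reasons related to safety or virologic failure*. The bullets then agree with exclusion (2). No new rule on failure status is needed, since SAP 4.2.3 already supplies it; a cross-reference would help the programmer.

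The cost is one line of text and one programming condition. The downside is that the CPSFU rates for SVR12 and SVR24 may come out slightly less favourable.

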4.1 Primary and Secondary Parameters

4.1.1 Primary Effectiveness Parameter

The percentage of patients achieving SVR12 (HCV RNA <50 IU/mL 12 weeks [i.e. 70 to 126 days] after the last actual dose of the ABBVIE REGIMEN).

Please note, in the study protocol no upper boundary for the time window was specified. The upper boundary of 126 days was introduced to achieve consistency with other studies investigating the ABBVIE REGIMEN ± ribavirin (RBV) for the treatment of CHC. For the handling of missing values see section 4.2.3.

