EoT	Actual EoT	Study day of last dose# (28 days prior to last dose - 7 days post last dose)
Post Treatment	12 weeks (SVR 12 window)	\geq 70-126 days post last dose
	24 weeks (SVR24 window)	127-210 days post last dose
	48 weeks\$	> 210 days post last dose

[^]values must also be \leq 7 days post last dose

\geq study day 2

*RVR = rapid virological response

\$ Please note that this time window is not specified in the study protocol, but added to consider possible relapse after day 210 in the analysis of the relapse rate. Analyses of SVR48 are not planned.

All reported safety laboratory test results will be assigned to one of the time points using the time windows specified in the table below.

Table 3 - Analysis Time Windows for Safety Laboratory Data

Phase	Time point	Time Window
Pre-Treatment	Baseline	Last value prior to start of study treatment (i.e. \leq study day 1)
Treatment Weeks	4 (day 29)	Study day during treatment period (Study day 1 = first treatment day)
	8 (day 57)	15 – 42 [^]
	12 (day 85)	43 – 70 [^]
	16 (day 113)	71 – 98 [^]
EoT	Actual EoT	Study day of last dose# (28 days prior to last dose - 7 days post last dose)
Post Treatment	4 weeks (28 days post last dose)	8– 56 post last dose
	12 weeks (84 days post last dose)	57 – 126 days post last dose
	24 weeks (168 days post last dose)	127 – 252 days post last dose
	48 weeks (336 days post last dose)\$	253 – 420 days post last dose

[^]values must also be \leq 7 days post last dose

\geq study day 2

\$ Please note that this time window is not specified in the study protocol, but added to consider possible reported values.

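### SAP 4.2.1 both keeps and excludes a viraemic patient whose end-of-treatment date is missing, and it does not say which rule governs the CPSFU rate for SVR12

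*SAP*

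**What the plan says.** **CPSFU.** SAP 4.2.1 gives three alternative ways for a CP patient to enter the CPSFU. The second is an HCV RNA of at least 50 "IU/mL at the last measurement post-baseline". It needs no treatment dates. A closing sentence, worded as a restatement of those criteria, then lists three excluded groups:

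1. patients with virological response at the last measurement but no sufficiently late value;
2. patients with no post-baseline value;
3. "patients with missing end of treatment date for reasons not related to safety or effectiveness, will be excluded from this analysis".

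Protocol 9.7.1 has only the first of these. Its sentence opens "This means only patients who had virological response at their last on-treatment or post-treatment" and contains no exclusion for a missing date.

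**Primary analysis.** SAP Table 2 places the SVR12 window at "70-126 days post last dose". SAP 4.2.3 states "HCV RNA values will be selected for an RVR, EOTR and SVR analysis based on visit windows as defined in Table 2". If a value is still missing after flanking and backward imputation, "the subject will be considered as virological failure at this time point". A missing last-dose date is not a ground for leaving the CP.

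**The concern.** The CPSFU repeats the primary SVR12 analysis as a sensitivity analysis. It is meant to set aside patients whose outcome is unknown for reasons unconnected with the drug. A patient whose last measurement shows virus is not such a patient, and both documents say in their inclusion criteria that this patient stays. If the programmer follows exclusion (3) instead, a non-responder leaves the denominator because of an administrative gap, and the sensitivity rate rises. The study expects 50-55 patients and few failures, so one patient is visible in the result.

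A related gap affects the primary rate. The SAP foresees patients without an end-of-treatment date, since it gives them their own exclusion, but it deals with them only in the CPSFU. For the CP the reader has to infer what happens.

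**Working it through.** The plan has no figure to reproduce: SAP 3.2 says the 50-55 is not statistically derived. The check is one of logic, followed by an illustration.

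**Step 1: does exclusion (3) follow from the inclusion criteria?** Exclusion (1) is confined to responders, so it cannot touch a patient who enters by criterion 2. Exclusion (2) concerns patients with no post-baseline value, so it cannot either. Exclusion (3) has no such limit. A patient with a last value of 50 IU/mL or more, and a date missing for an administrative reason, meets criterion 2 and exclusion (3) together. No order of precedence is given. The SAP marks its 126-day upper limit and its added late windows as departures from the protocol, but not exclusion (3).

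**Step 2: which date?** SAP 4.1.2 defines EoT by the last intake of either the ABBVIE REGIMEN or ribavirin. SAP 4.1.1 counts SVR12 from the last ABBVIE REGIMEN dose alone. Exclusion (3) refers to the end-of-treatment date. If only the ribavirin stop date were missing, the SVR12 window could still be placed, yet (3) might be applied.

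**Step 3: what happens in the CP?** Values reach the SVR12 analysis through a window counted from the last dose. SAP 4.2.3 says "No data will be imputed for any effectiveness or safety analyses except for the analyses of the HCV RNA endpoints" and certain PRO endpoints, and nothing supplies a missing date. With no date, neither the window nor the flanking and backward imputation around it can be placed, so the value remains missing and the default is failure. This is an inference from the rules; the SAP does not state it.

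**Step 4: size.** Assumptions: all enrolled patients are in the CP; 3 are true failures (a rate near 94-95%, within the 90-100% of protocol Table 1); the number of undated patients is unknown. With s responders among n patients:

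- dropping j viraemic patients changes the CPSFU rate from s/n to s/(n − j);
- scoring k cured patients as failures changes the CP rate from s/n to (s − k)/n, a loss of k/n.

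Intervals are two-sided 95% Wilson score, as in SAP 4.2.7.1: centre (p + z²/2n)/(1 + z²/n), half-width z√(p(1 − p)/n + z²/4n²)/(1 + z²/n), z = 1.96.

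| Case | n = 50 | n = 55 |
|---|---|---|
| True rate | 47/50 = 94.0% (83.8-97.9) | 52/55 = 94.5% (85.1-98.1) |
| CPSFU, 1 viraemic dropped | 47/49 = 95.9% (86.3-98.9) | 52/54 = 96.3% (87.5-99.0) |
| CPSFU, 2 viraemic dropped | 47/48 = 97.9% (89.1-99.6) | 52/53 = 98.1% (90.1-99.7) |
| CPSFU, criterion 2 governs | 94.0%, unchanged | 94.5%, unchanged |
| CPSFU, 1 cured dropped | 46/49 = 93.9% (83.5-97.9) | 51/54 = 94.4% (84.9-98.1) |
| CP, 1 cured scored failure | 46/50 = 92.0% (81.2-96.8) | 51/55 = 92.7% (82.7-97.1) |

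The loss per cured patient in the CP is 1/50 = 2.0 points or 1/55 = 1.8 points.

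**Step 5: can one patient distort both rates?** If the undated patient was cured, the CP rate is too low by 1/n and the CPSFU rate hardly moves. If the patient was viraemic after treatment, failure is the correct CP score, and only the CPSFU rate can be wrong. The two errors fall on different patients.

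**The case against.** The strongest reply is that the SAP does not fix either outcome. The exclusion sentence presents itself as an explanation of the inclusion criteria, so criterion 2 can be taken to prevail and the viraemic patient stays. Exclusion (3) is also conditional: a date missing because of an adverse event or non-response is not caught. This stands, and it makes the CPSFU problem an unresolved contradiction. A reader might infer that the SAP definitely drops viraemic patients; it does not settle that.

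On the CP, backward imputation moves a value lying after the SVR window into it. A negative result drawn very late would lie after the window under any plausible date, so an analyst might credit it. A reader might infer that an undated patient fails whatever the HCV RNA shows; the SAP never says so. Failure is still the more natural reading, because the window has no position without a date. Counting missing values as failures is also prespecified, and protocol 9.9 acknowledges that missing data can lower the SVR rate.

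Safeguards exist: an EoT page for early stoppers (protocol 9.2.3), eCRF checks and queries (protocol 9.6.1), and tabulated reasons for exclusion from each population (SAP 4.2.5). They make missing dates rarer and CPSFU exclusions visible. They do not say which rule applies, and nothing in them counts CP patients who fail only for want of a date.

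Finally, putting a scheduled date in place of the actual last dose is debatable, since SAP 4.2.7.2.1 allows for courses more than 7 days short or long. This stands, and it is why a derived date belongs in a sensitivity analysis.

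**Conclusion.** The contradiction in SAP 4.2.1 is real and lies in the text: criterion 2 and exclusion (3) give opposite answers for a viraemic patient with an administratively missing date, and exclusion (3) departs from protocol 9.7.1 without being marked as a change. On the literal reading, each such patient dropped raises the CPSFU SVR12 rate by about 2 points under the assumed counts.

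The CP point is secondary. Failure scoring is implied, and it understates the rate only for patients who were in fact cured.

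A reader might infer that one missing date biases both SVR12 rates in opposite directions. The documents do not support that, because the two errors need patients with opposite outcomes. The documents give no count of missing dates; it may be zero, and then neither rate is affected.

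**What to change.** - **CPSFU.** Limit exclusion (3) to patients whose last post-baseline HCV RNA is below 50 IU/mL, so that criterion 2 governs. State whether the date meant is the last ABBVIE REGIMEN dose, which anchors SVR12, or the last intake of either that regimen or ribavirin.
- **CP.** Keep the primary rule that a missing value counts as failure, and say that it covers a missing last-dose date. Report the number of such patients.
- **Sensitivity analysis.** For those patients, assign HCV RNA values from a derived last-dose date: the EoT visit date or, failing that, first dose plus scheduled duration, or the last date known on treatment if later. Flag each derived date in a listing.

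The cost is a few sentences in the SAP and minor programming. The small downside is one assumed date per affected patient, confined to the sensitivity analysis.
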